10.2.3. Intensity Grading of Adverse Events

Adverse events and their severity will be assessed based on *National Cancer Institute Common Terminology Criteria for Adverse Events* (NCI-CTCAE, version 4.0). These criteria can be consulted at the following address:

http://evs.nci.nih.gov/ftp1/CTCAE/CTCAE_4.03_2010-06-14_QuickReference_8.5x11.pdf

10.2.4. Serious Adverse Events (SAEs):

A serious adverse event (SAE) or reaction is any harmful medical event that, regardless of the dose:

- Results in the death of the patient.
- Is life-threatening to the patient or potentially fatal (i.e., the patient is at immediate risk of death at the time of the event).
- Requires patient hospitalisation or the prolongation of existing hospitalisation.
- Results in permanent or significant disability or incapacity.
- Causes a defect, congenital malformation or results in cancer.

In addition, medical and scientific judgement should be used to decide whether other situations should be considered as a serious adverse event, although they do not meet the above criteria, such as those that endanger the patient's life or require intervention to prevent any of the above outcomes.

It must not be confused with the term "severe", which indicates the intensity of the adverse event.

Recording and Reporting of Serious Adverse Events (SAEs):

Information on SAEs, whether related to the treatment or not, will be collected and recorded on the SAE form of the corresponding case report form. SAEs, as defined above, must be recorded from the date the informed consent form was signed, and the pharmacovigilance contact person must be notified immediately, within 24 hours of awareness by the study site, by fax to

Marketing Farmacéutico & Investigación Clínica

The initial report must state the site name and number, the name of the investigator, the patient ID number and initials, patient demographics, study drug administration data and everything known about the serious adverse event, including date of onset, intensity, treatment and relationship to the study drug. If the patient dies, the report should include the cause of death and its potential relationship to the study drug, in addition to the autopsy findings (if available).

This includes the determination of one or more SAE criteria, a detailed description of the event, relevant clinical reports (without names or other patient identifiers), the date of death and an autopsy report (where applicable, and if available), the updated investigator assessment regarding the relationship of the study drug to the SAE, and actions taken.

The Sponsor will send the safety reports to the health authorities in an appropriate manner, in accordance with the applicable laws and regulations.

SAEs must also be reported by the investigator to the responsible Independent Ethics Committee (IEC), in accordance with regulatory requirements.

The assessment of the expected SAEs considered to be reportable to the health authorities and Ethics Committees, which were specified above, will be carried out by the Sponsor in accordance with the "Guide for the investigator" section of the most up-to-date version of the Investigator's Brochure for TH-302. The updated version of the Investigator's Brochure will be provided by Threshold.

The notification of a suspected SAE must not be delayed in order to obtain further information. The follow-up report will be completed with the collection of any additional data after the initial report. This report will also be issued should the event be resolved, in the absence of significant changes, or should the situation stabilise. This report will be issued in the following 24 hours.

Through the study's principal investigator, the sponsor (GETNE) will assess the SAEs, taking into account the product safety reference documents, and will report, through the CRO, those SAEs that meet the expedited reporting criteria (serious, unexpected and related to the study medication) with the help of the monitor. The sponsor is responsible for notifying the competent authorities (Spanish Agency of Medicines and Medical Devices - AEMPS, central IEC, hospital IEC, competent bodies of the Autonomous Communities) and the principal investigators/institutions involved in the study, and this will be carried out within the time scales determined by current Spanish legislation. The maximum period for notification shall be 15 calendar days from the time the sponsor learns of the suspected adverse reaction. However, if the unexpected serious adverse reaction leads to the patient's death, or endangers the patient's life, the sponsor shall inform the AEMPS within 7 calendar days from the time it became aware of the situation. Said information shall be completed, as far as possible, within the following 8 calendar days.

All SAEs will undergo a follow-up until the following situations are reached:

- Event resolution
- Event stabilisation.
- Restoration of the baseline situation and, if available, a baseline value.
- The event can be attributed to products other than the study treatment or factors not related to the study.
- It is not possible to obtain further information.

All unresolved SAEs at the conclusion of the study must be followed up, to determine the end result.

SAEs will be recorded from the time the patient signs the informed consent form until the follow-up safety visit, 28 days after the last dose of the study drug, or until the start of administration of an investigational or medical drug, whichever comes first.

Fatal events (regardless of their relationship to the study drug) will be recorded as serious adverse events up to the follow-up safety visit (28 days after discontinuation of the study drug) or until the start of further treatment, whichever comes first. Fatal events that occur after the follow-up safety visit (28 days after discontinuation of the study drug) or upon initiation of an investigational or medical drug, whichever comes first, will not be recorded as serious adverse events but will be recorded on the corresponding case report form.

In the event of death, the main cause of death (the event that led to death) should be recorded and reported as an SAE. The result of this event will be recorded as "Fatal"; the death will not be recorded as a separate event. It may only be notified as an event if there is no cause of death (for example: sudden death, unexplained death). In this case, the death in itself could be reported as an SAE.

This event will not be reported expeditiously as an SAE within 24 hours, but will be recorded in the case report form and analysed as a study objective. The death of a patient is not an adverse event in itself, but an outcome of an adverse event. All patient-death reports must include an adverse event as a cause of death (if known).

The sponsor will inform the investigators as soon as possible of any safety information that might affect patients.

Reporting pregnancy

Women of childbearing potential who are sexually active must use an effective contraception method during the course of the study, so as to minimise the risk of failure. Before enrolment in the study, women of childbearing potential will be informed of the importance of avoiding pregnancy during their participation in the study, and the potential risk factors of an unwanted pregnancy.

All women of childbearing potential **MUST** have a negative pregnancy test within 7 days prior to enrolment.

In addition, all women of childbearing age will be asked to immediately contact the investigator if they suspect they might be pregnant (e.g., missed or late menstrual period) at any time during their participation in the study.

If, after initiating administration of the investigational medicinal product, it is discovered that a study patient is pregnant or may have been pregnant at the time of exposure to the product, the investigational medicinal product will be permanently discontinued as appropriate (e.g., dose reduction if required for the safety of the patient). The investigator must immediately inform the sponsor of this event in accordance with the SAE reporting procedures, and the pregnancy must be recorded on a pregnancy form (Annex 7).

Initial information on a pregnancy must be reported immediately to the sponsor and information about its outcome must be provided once it is known. Completed pregnancy follow-up forms must be sent to the sponsor, in accordance with the SAE reporting procedures.

The sponsor must be informed of any pregnancy that occurs in a female partner of a male study participant. Information on this pregnancy will be collected on the pregnancy form (Annex 7).

Pregnancies must be reported to:

Marketing Farmacéutico & Investigación Clínica

The treatment discontinuation and follow-up procedures laid down in the protocol must be applied to the patient, unless contraindicated for pregnancy (e.g., x-rays). If indicated, other appropriate pregnancy follow-up procedures will be considered.

A phase II trial to assess the activity and safety of TH-302 in combination with sunitinib in patients

In addition, the investigator must inform the sponsor of any pregnancy, and follow-up on information regarding the course of the pregnancy, including a perinatal and neonatal outcome. Infants should be monitored for a minimum of 8 weeks

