10.2 Safety Assessment

10.2.1 Safety Analysis

The safety period runs from the date of the signature of the informed consent form until 28 days after the last dose of the study drug. Safety will be evaluated according to adverse event reports, the frequency of treatment discontinuations due to adverse events, and laboratory or ECG tests. Descriptive analysis will be used.

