All adverse events experienced by patients, regardless of their relationship to the study drug, must be reported in full on the adverse event page of the case report form and in the patient’s medical record, adopting the appropriate medical terminology. The severity, the result and relationship to the study drug will be determined and documented in the case report form.

Should a patient discontinue the study drug due to an adverse event, this must be recorded in the case report form. In the event of patient death caused by disease progression, the data will be included in the efficacy analysis, unless the investigator feels that the event is related to the study medication. Adverse events will be monitored until they have been resolved, or until they have stabilised and/or reached a new baseline level. If an adverse event has not been resolved before the end of the study, the investigator and the medical monitor will perform a clinical assessment to determine whether its follow-up is justified.

The site investigator must record all directly observed adverse events and all adverse events that were spontaneously reported.

It should be noted that the intermittent or on-demand use of any medicine (and specifically any newly-prescribed medication) throughout the study could precipitate the onset of an adverse event that would have to be recorded on the case report form, both on the adverse event form as well as the concomitant medication form.

Adverse events will be recorded on the case report form from patient enrolment after the informed consent form has been signed, during the study treatment and 28 days following the end of treatment. During the long-term follow-up, following the 28-day period after the end of treatment, adverse events (AEs) related to the study treatment or procedures will be recorded, even after study completion, until stabilisation or until the outcome is known, unless the subject is documented as “lost to follow-up”. In addition, should the patient sign the informed consent form but not receive treatment, adverse events will be recorded that the investigator considers to be related to the study procedures.

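### SAE recording can close before day 28 when a new drug starts, but AE recording does not, so SAEs can be under-counted and related ones can miss the reporting route

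*Protocol*

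**What the plan says.** **SAEs (Protocol 10.2.4).** The first instruction gives a start but no end: "SAEs, as defined above, must be recorded from the date the informed consent form was signed". Later the same section sets an end at the 28-day safety visit, and then adds an earlier stop: "or until the start of administration of an investigational or medical drug, whichever comes first".

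**Fatal events (Protocol 10.2.4).** Deaths are SAEs up to the 28-day safety visit "or until the start of further treatment, whichever comes first". The next sentence describes the same cut with the broader drug wording used for SAEs. Deaths after it "will not be recorded as serious adverse events but will be recorded on the corresponding case report form".

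**AEs (Protocol 10.2.2).** All AEs are recorded from enrolment after consent, "during the study treatment and 28 days following the end of treatment". After that, "adverse events (AEs) related to the study treatment or procedures will be recorded, even after study completion", until the event stabilises or its outcome is known. A new drug does not end either period.

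**Safety analysis.** Protocol 10.2.1 and SAP 1.5.3 both define the safety period as running "from the date of the signature of the informed consent form until 28 days after the last dose of the study drug". Protocol 9.1 and SAP 1.5.5.1 take AEs for analysis up to 28 days after treatment is completed, and list AEs and SAEs together as outputs. None of these four places mentions an earlier stop for SAEs.

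**The concern.** Every SAE is also an AE, so the two sets of rules apply to the same event and can disagree about it. When a new therapy begins before day 28, 10.2.2 still requires the event to be recorded while 10.2.4 says it is no longer an SAE. Beyond day 28, 10.2.2 keeps treatment-related AEs, whereas 10.2.4 says nothing about treatment-related SAEs.

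Two things are at stake. The first is the SAE tally. Safety is part of the trial's main purpose (Protocol 1.12), and in a single-arm trial of 43 planned patients there is no comparator subject to the same shortfall. The second is the reporting route. The SAE form, notification within 24 hours and the sponsor's assessment for expedited reporting all start from an event being handled as an SAE.

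The trigger is also undefined. *Medical drug* is not limited to any class, and the parallel sentence speaks of *further treatment*. Ten sites could apply it in different ways.

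**Working it through.** The plan gives no figure to reproduce. The check sets the windows side by side and follows single events through them.

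| Place | What it governs | Latest end | Stops at a new drug? | Related events afterwards |
|---|---|---|---|---|
| Protocol 10.2.1, SAP 1.5.3 | safety period | day 28 after last dose | no | not stated |
| Protocol 10.2.2 | AE recording | day 28 after end of treatment | no | yes, to stabilisation or known outcome |
| Protocol 9.1, SAP 1.5.5.1 | AE analysis | day 28 after completion | no | not stated |
| Protocol 10.2.4 | SAE recording | day 28 after last dose | yes | no provision |
| Protocol 10.2.4 | death counted as SAE | day 28 after stopping | yes | no; case report form only |

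**Can the stop apply before day 28?** Yes. Protocol 6.2 leaves a further systemic treatment after withdrawal for toxicity to the investigator and states no minimum interval. Protocol 11.5 puts the end-of-treatment visit 4 weeks after stopping, so a new drug can start before it. The same holds for a patient who progresses and moves on to another therapy.

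**Three events, taking the text as written (days are illustrative).**
1. New therapy on day 14, serious non-fatal event on day 20. Under 10.2.2 it is an AE to record. Under 10.2.4 it is not an SAE.
2. No new therapy, treatment-related serious event on day 40. Under 10.2.2 it is recorded as a related AE. It lies outside the SAE period in 10.2.4.
3. New therapy on day 14, death on day 20. It is recorded on the case report form and counts for overall survival, but not as an SAE.

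**How much of the window closes.** If a new therapy starts on day d after the last dose, the share of the 28-day window without SAE recording is (28 − d)/28. The day d is an assumption, because the documents give none.
- d = 7: 21/28 = 75%
- d = 14: 14/28 = 50%
- d = 21: 7/28 = 25%
- d = 28 or later: 0%

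The AE window stays at 28/28 throughout. These are shares of time at risk, not of events.

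**What one missed classification does.** If all 43 planned patients are analysed, one patient whose only SAE is not classified as such lowers the proportion with an SAE by 1/43 = 2.3 percentage points.

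**Can the SAE count be rebuilt from the AE page?** Not with certainty. Protocol 10.2.2 lists seriousness among the things AE assessment covers, but its recording instruction names only severity, result and relationship. Protocol 10.2.4 itself warns that serious and severe are different things, so grade is no substitute. In the SAP the only adverse event table shell (Table 34) is by grade 1 to 4, and the index of tables lists no SAE table.

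**The case against.** The best argument for the rule is attribution: once another therapy starts, later events may belong to that therapy, and stopping SAE recording keeps them out of the study treatment's account. That is a legitimate aim. It stands as a reason to separate such events, but not as a reason to leave them out of the SAE process while recording them as AEs.

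There are also limits on how far the point goes, and they stand. A reader might infer any of the following, which the documents do not support:
- **That events or deaths are lost.** Non-fatal events remain due on the AE page, and hospitalisations and deaths are separate safety outputs (Protocol 9.1, SAP 1.5.5.1). Late deaths go on the case report form and count for overall survival.
- **That any new medicine closes SAE recording, so nearly every patient is affected.** The words permit this, but the parallel use of *further treatment* points to subsequent therapy. Read literally, an antiemetic given with TH-302 (Protocol 6.1.2) would end SAE recording during study treatment, which cannot be intended.
- **That patients withdrawn for toxicity switch at once and carry the highest risk of a serious event.** Protocol 6.2 gives no timing, and nothing in the documents supports the risk claim. Patients who progress are affected in the same way.
- **That related late SAEs are definitely dropped.** An SAE is an AE, and the opening instruction in 10.2.4 has no end date, so a site could follow 10.2.2 and keep them. The text conflicts; it does not settle the matter.

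**Conclusion.** The inconsistency is real. As written, 10.2.4 can close SAE recording, and the counting of deaths as SAEs, earlier than every other safety window in the two documents, and it makes no provision for related SAEs afterwards. SAEs can therefore be under-counted relative to AEs in any patient who starts a new therapy within 28 days of the last dose. A related serious event can also miss the SAE form, the 24-hour notification and the expedited assessment.

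The direction is certain: relative to the AE window, the SAE count can fall but not rise. The size is unknown. It depends on how many patients start a new therapy before day 28, how many of them then have a serious event, and which of the conflicting instructions each site follows. The documents give none of these. The effect is on classification and reporting rather than on capture of the event, and the primary response-rate analysis is untouched. The change should be made, but the point does not show that the trial's SAEs were in fact under-counted.

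**What to change.** - **One window.** Reconcile Protocol 9.1, 10.2.1, 10.2.2 and 10.2.4 with SAP 1.5.3 and 1.5.5.1, so that AEs, SAEs and fatal events are all recorded from consent to 28 days after the last dose regardless of new therapy.
- **Related SAEs later.** State in 10.2.4 that SAEs related to study treatment or procedures are recorded and reported at any later time, matching the AE rule.
- **A defined term used only as a flag.** Replace *medical drug* and *further treatment* with one defined term for subsequent anticancer therapy. Record its start date and use it to mark events, not to end recording.
- **SAP output.** Add an SAE table that shows SAEs with and without events after the flag.

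The cost is a short protocol amendment, a matching SAP edit and a few more SAE forms. Some of the added events will be attributable to the next therapy; the flag shows which ones may be. Protocol 7.3 and 11.6 already provide for collecting later cancer treatment, so little new data is needed.

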6.3. Titration of the Study Drug

All dose modifications must be conducted according to the most severe preceding toxicity, as classified by the *National Cancer Institute Common Terminology Criteria for Adverse Events* (NCI-CTCAE, version 4.0).

As far as possible, an attempt should be made to follow the dose and scheduled regimen. However, in case of an adverse event, administration of the study drug should be titrated as described below.

The patient should notify the investigator of the date of onset of any adverse signs and symptoms.

Dose modifications to both treatments may be required in 3 different situations:

- During a cycle: treatment is discontinued until recovery and the dose is reduced, if necessary, during a particular treatment cycle.
- Between different cycles: treatment administration is delayed in the next cycle due to persistence of residual toxicity at the beginning of a new cycle.
- During the following cycle: the dose is reduced in the following cycle, taking into account the toxicity exhibited in the previous cycle.

In the event of treatment delay, proceed as follows:

- On day 1 of a cycle, if the administration of sunitinib must be postponed, the whole cycle must be delayed.

A phase II trial to assess the activity and safety of TH-302 in combination with sunitinib in patients

- On days 8 or 22, if the administration of both drugs must be postponed, that dose must be skipped.
- On days 8 or 22, if the administration of just 1 drug must be postponed, that dose will be skipped and the cycle will not be delayed, but rather the other drug will be administered on its own.

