6.3.1. Discontinuation of Treatment

The treatment will be temporarily discontinued until the resolution of \leq grade 2 toxicity. Depending on the duration of treatment discontinuation, this will either lead to the loss of all subsequent scheduled doses within the same cycle, or even delay the start of the next cycle. If the patient recovers from the adverse event within the same cycle, therapy may be continued in that cycle. Any missed doses for toxicity will not be made up for within the same cycle.

Dose reduction when reintroducing the treatment is determined below (section 6.3.3), unless, in the event of disagreement, the investigator prefers to discuss it with GETNE [contact]. If a dose is reduced within a cycle, the patient should return to the site to receive the new treatment dose.

If treatment discontinuation lasts $>$ 4 weeks, for reasons other than study treatment toxicity (non-cancer surgery, etc.), GETNE must be consulted before reintroducing the study drug

Treatment will be discontinued permanently in the following situations:

- The patient requires more than 2 dose-reduction steps.
- The patient requires more than 4 weeks delay (one full cycle) to restart treatment due to study treatment toxicity.

In patients for whom recovery from treatment toxicity involves treatment suspension lasting more than 4 weeks, or delaying a treatment cycle, but there is a clear clinical benefit in the opinion of the investigator, reintroduction of the treatment may be discussed with GETNE

Patients who discontinue treatment with TH-302 may continue receiving sunitinib as monotherapy within the trial.

Under no circumstances may patients receive TH-302 as monotherapy. In the event that the administration of sunitinib must be discontinued, the administration of TH-302 will also be discontinued.

Patients who permanently discontinue TH-302 and sunitinib will abandon active treatment and enter the follow-up phase.

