6.3.3. Dose Reduction

Titration is not required in patients with grade 1 or 2 treatment-related toxicity. Despite this, investigators should always treat their patients according to their medical judgement and based on individual circumstances.

2 dose-reduction steps are permitted depending on the type and severity of toxicity. If the investigator deems it to be necessary, the reduction of the two dose levels can be performed directly, without needing to wait for a time between both.

Patients requiring more than 2 dose reductions will abandon the treatment phase and enter the follow-up phase.

All adjustments or dose modifications should be clearly documented in the patient's medical record and in the CRF (Investigational product administration).

Once a patient's dose has been reduced, all subsequent cycles will be administered at that same dose, unless a further reduction is required. Dose reescalation will not be permitted as part of the study. Specific cases will be discussed with the study's coordinating investigator [REDACTED]

Table 1. Available dose levels with TH-302 and sunitinib

DOSE LEVEL	TH-302 DOSE	SUNITINIB DOSE
Starting	340 mg/m ² D8, 22	37.5 mg/24h D1-28
-1	280 mg/m ² D8, 22	37.5 mg/24h D1-28
-2	280 mg/m ² D8, 22	37.5 mg/24h D1-22, plus a rest week (3 weeks on / 1 week off)

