14. Chronic obstructive pulmonary disease (COPD) or any lung disease accompanied by hypoxaemia or oxygen saturation < 90% after a 2-minute walk.
15. Current treatment with therapeutic doses of acenocoumarol (administration of low doses of acenocoumarol up to 2 mg/24 h for deep vein thrombosis prophylaxis is permitted).
16. Known human immunodeficiency virus (HIV) infection.

17. Pregnant or breast-feeding. All female patients of childbearing age must have a negative pregnancy test (blood or urine) prior to study enrolment.
18. Prior allergic reaction to ingredients structurally similar to TH-302 or sunitinib or to any of the drugs' excipients.
19. Non-healing wound, fistulae, active stomach ulcer or bone fractures.
20. Any condition (medical or psychiatric) or reason that, in the opinion of the investigator, would interfere with the patient's ability to participate in the clinical trial, by placing the patient at excessive risk or by complicating the interpretation of the safety data, therefore being unsuitable for enrolment in the study.

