5. Clinical chemistry: AST, ALT, GGT, alkaline phosphatase, direct and total bilirubin, urea, calcium, chloride, creatinine, glucose, LDH, phosphorus, magnesium, potassium, sodium, albumin at the baseline visit (≤ 7 days) and at each pre-treatment visit (± 3 days prior to day 8 and ± 1 day prior to day 22 of each cycle). It will also be conducted ± 1 day prior to day 15 to ensure a weekly follow-up of the patients.
6. Enolase 1, chromogranin A (or peptide secreted functionally) tumour markers at baseline visit, every 8 weeks (± 1 week) and at the end-of-study visit.
7. Urine and blood pregnancy test in female patients of childbearing age. This will be conducted within 7 days prior to the day 1 visit and whenever pregnancy is suspected.
8. 12-lead electrocardiogram: before every test, the subject must be at rest for approximately 10 minutes. The subject should be in a semi-lying or supine position; the same position must be adopted for all subsequent ECG tests.
In the first cycle, an ECG will be performed at day 8 and at day 22 immediately after completion of the TH-302 infusion. Thereafter, an ECG will be performed at the discretion of the investigator
9. Baseline and end-of-study visit echocardiogram, and if clinically indicated.
10. Thoracic, abdominal, and pelvic CT scan within 28 days prior to study enrolment and subsequently every 8 ± 1 weeks and at the end-of-study visit. For tumour reassessments, the same exploratory technique used in the baseline examination must be adopted. A baseline bone scan may be performed within 28 days prior to day 1 of the first cycle, if there is a clinical suspicion of bone metastases. In the event of bone metastases, a reassessment bone scan will be performed every 12 weeks until week 24 and thereafter every 24 weeks until the end of treatment. Margin of ± 14 days with reference to the scheduled visit.
An MRI may only be performed in exceptional circumstances and only in cases when a CT scan is not possible.
11. Blood sample for the analysis of genetic markers that will be sent to [REDACTED]. Only the tubes from the baseline visit will be sent.

A phase II trial to assess the activity and safety of TH-302 in combination with sunitinib in patients

12. Paraffin-embedded tumour sample for marker analysis that will be sent to [REDACTED]
[REDACTED]

13. Determination of overall survival of patient (living/death/lost to follow-up). According to the site's usual practices, until the end of the trial.

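### The pregnancy rule orders permanent discontinuation but qualifies it and gives dose reduction, which is not a discontinuation, as its only example

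*Protocol*

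**What the plan says.** The instruction is in Protocol 10.2.4, under Reporting pregnancy. It applies once dosing has begun and "it is discovered that a study patient is pregnant or may have been pregnant at the time of exposure to the product". In that event the investigational medicinal product "will be permanently discontinued as appropriate (e.g., dose reduction if required for the safety of the patient". The investigator must also inform the sponsor immediately through the SAE procedures.

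A little further on, the same section adds: "The treatment discontinuation and follow-up procedures laid down in the protocol must be applied to the patient", except where pregnancy rules out a procedure, such as an x-ray.

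Other parts of the protocol aim to keep pregnant patients off treatment. Exclusion criterion 17 in section 7.2 reads: "Pregnant or breast-feeding. All female patients of childbearing age must have a negative pregnancy test (blood or urine) prior to study enrolment". Note 7 to the schedule in Annex 1 says of the pregnancy test: "This will be conducted within 7 days prior to the day 1 visit and whenever pregnancy is suspected". Section 10.2.4 also requires effective contraception and asks women to contact the investigator immediately if they suspect pregnancy.

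The SAP mentions pregnancy only when it repeats the exclusion criterion (1.4.1.2).

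**The concern.** The sentence gives an order and then an example that does not carry it out. Permanent discontinuation ends exposure, whereas a dose reduction lowers it and lets it continue. The words *as appropriate* add discretion, and the stated condition for using it is the safety of the patient, with no mention of the fetus.

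Investigators will look for this instruction at short notice and may apply it as written. Section 3.4 describes the active metabolite of TH-302 as a DNA alkylating agent, and sunitinib is a tyrosine kinase inhibitor. If the example is followed, a patient known to be pregnant could go on receiving both. That would undercut the exclusion, contraception and testing rules elsewhere in the protocol.

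**Working it through.** No arithmetic applies. The check is whether any other text resolves the conflict inside the sentence.

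1. **Does the protocol treat reduction and discontinuation as different things?** Yes. Under 6.3.3, after a reduction, "all subsequent cycles will be administered at that same dose, unless a further reduction is required". Section 6.3.1 treats permanent discontinuation as a separate outcome, reached for example when a patient would need more than 2 reduction steps. Section 6.3.3 deals with toxicity and 10.2.4 does not cite it, so it shows how the protocol uses the term; it does not set a dose for a pregnant patient.

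2. **Could the parenthesis mean stepping down on the way to stopping?** It could, since it is conditional on patient safety. But no taper is defined for either drug, and a step-down would itself prolong exposure.

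3. **Do the stopping lists settle the matter?** No. Pregnancy is not named in the treatment-duration reasons in 6.2, the permanent-discontinuation situations in 6.3.1 or the withdrawal criteria in 7.3. Section 6.2 does allow stopping at the investigator's discretion, but that permits a stop without requiring one.

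4. **Does the later sentence in 10.2.4 settle it?** Only in part. It presupposes that treatment ends, so it supports stopping. It refers back to procedures that do not name pregnancy, and it does not withdraw the example.

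5. **Does the singular product leave one drug out?** Probably not. Section 6.3 is headed in the singular and then says: "Dose modifications to both treatments may be required in 3 different situations". Section 6.3.1 adds: "In the event that the administration of sunitinib must be discontinued, the administration of TH-302 will also be discontinued". Section 6.3.1 also lets a patient who stops TH-302 continue on sunitinib alone, so naming both drugs in the pregnancy rule is a useful clarification. The singular is not a separate error.

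**Result.** The sentence in 10.2.4 is the only explicit dosing instruction for a pregnancy found on treatment, and nothing visible corrects its example.

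**The case against.** The best reply is that the operative verb already orders a permanent stop and the next part of the section assumes one. On that view the parenthesis is an awkward aside, limited to cases where patient safety requires it, and the sentence is under-specified rather than contradictory. The English may also be a translation, so a slip is possible, though this cannot be confirmed. The practical safeguards are real: exclusion at entry, contraception, testing on suspicion and immediate notification of the sponsor.

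Most of this stands. The main direction is to stop, and prolonged exposure is unlikely. It does not remove the fault, because a safety instruction should not depend on the reader setting aside its only example.

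Three stronger readings are tempting, and the documents do not support them:

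- A reader might infer that the protocol sets out to keep pregnant patients on treatment, perhaps at the reduced levels in Table 1. The order to discontinue points the other way, and nothing links the pregnancy sentence to Table 1.
- A reader might think it wrong to give one instruction both for a current pregnancy and for possible pregnancy at exposure. Applying permanent discontinuation to both is a defensible conservative choice.
- A reader might conclude that treatment must also stop on mere suspicion, or that rules for resuming are missing. The protocol requires contact and a test on suspicion. A mandatory stop at that point would be a new treatment rule and is not needed to correct this sentence.

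**Conclusion.** The wording is wrong as it stands. It orders permanent discontinuation and then offers, as its only example, an action that is not a discontinuation. Read literally, it could allow continued dosing at a reduced dose during pregnancy.

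The error is minor in frequency but concerns patient safety. It can affect only women of childbearing potential among the 43 planned patients. The documents give no figure for how many that is or for the chance of pregnancy, so no rate is offered; few or no cases are expected. The response endpoint, sample size, error rates and analyses are untouched.

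The conclusion rests on the visible text. The consent pages were removed, and the pregnancy form in Annex 7 appears only as a heading, so an instruction there could not be checked.

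**What to change.** In the pregnancy paragraph of 10.2.4, delete the qualifier *as appropriate* together with the whole parenthesis, and name the drugs. The sentence would then say that, in the two circumstances it already describes, TH-302 and sunitinib will both be permanently discontinued.

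Optionally, add pregnancy to the permanent-discontinuation situations in 6.3.1 and the withdrawal criteria in 7.3, so that all three places agree.

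Nothing further is needed. A mandatory stop on suspicion would add a rule. A case-by-case decision for possible past exposure would loosen the present one. A resumption rule would have to be reconciled with the 4-week delay criterion in 7.3.

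The cost is an edit to one sentence, plus one line in each of two lists if the option is taken. The design, sample size, visit schedule and SAP do not change.
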